6.2.9.5 Occurrence and Severity of Dyspareunia

Pain with intercourse will be recorded daily by the subject in the e-diary and collected as missed diary review data in the CRF during monthly contact when not entered by the subject within the 10 day window. The occurrence and severity of dyspareunia will be summarized for each cycle in safety and ECYC population. The summary will present the number of days in each cycle with dyspareunia. The worst pain grade and the highest frequency occurrence pain grade in each cycle will be summarized using shift tables to assess changes from baseline. The missing value imputation at cycles will be calculated similarly as the above Section 6.2.9.4.

All occurrence and severity of dyspareunia e-diary data and daily missed diary review data from monthly contact will be presented in data listings.

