#### **8.1 Inclusion**

Subject must meet all of the following criteria to participate in this study:

1. Between 18-40 years of age at the time of study initiation;
  - 1.1 Enrollment will be targeted for 225 subjects aged 18-35 (for safety and effectiveness analyses) and an additional 25 subjects aged 36-40 (for safety only); (note: all subjects will be included in the analysis for device placement and tolerability);
2. Pre-menopausal, as determined by regular menstrual cycle ( $28 \pm 7$  days) for the last 3 months;
  - 2.1 Based on patient history when not on hormonal contraceptives;
3. Sexually active with a male partner who has not had a vasectomy;
4. Reasonably expect to have coitus at least once monthly during the study period
5. In a mutually monogamous relationship of at least 3-6 months duration
6. Seeking to avoid pregnancy for the next 12 months;
7. Willing to use the study device as the sole form of contraception;
8. Willing to accept a risk of pregnancy;

9. Subjects who are age 21 or older, at time of informed consent, must have a normal PAP or ASC-US with negative high risk HPV test result within the appropriate screen timeframe, and prior to LevoCept insertion;
10. Able and willing to comply with all study tests, procedures, assessment tools and follow-up; and
11. Able and willing to provide and document informed consent and Authorization to Release Protected Health Information (PHI).

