4.1 Efficacy Variable

The primary outcome measure is effectiveness and will be evaluated as absence of pregnancy during study device use.

E-Diary data from the day of study placement to end of study/exit will collect the following information:

- 1) Menstrual and intermenstrual bleeding;
- 2) Vaginal intercourse;
- 3) Pain with intercourse;
- 4) Use of additional contraception;
- 5) Menstrual pain or cramping;
- 6) LevoCept expulsion

When data is still missing for a day after final attempt to have subject complete E-Diary, Vaginal intercourse, Pain with intercourse and Use of additional contraception will be collected for that specific missing day during monthly contact. The CRF collected data is used as a back-up. It is always preferred for the subject to complete the E-Diary data. If it occurs for a particular day that there is both subject data and CRF collected data, the subject data will take precedence and be used.

1. Pearl index

The primary efficacy variable is Pearl index. The Pearl index based on 28-day cycles and defined as the number of pregnancies per 100 woman-years (with one year comprising 13 28-day cycles). It will be calculated as:

$$\text{Pearl index} = \frac{N \times 1300}{L} = \frac{\text{Number of pregnancies} \times 1300}{\text{Number of woman-cycles of pregnancy at risk}}$$

Where n is the number of pregnancies, L is the number of woman-cycles of pregnancy at risk.

Only pregnancies judged to have occurred during study device use, or for which the estimated date of conception was within 7 days after study device removal or calculated date of expulsion are counted.

The number of woman-cycles of pregnancy at risk is the sum of the number of 28-day cycles for each subjects from the date of study device successful placement through the date of study device removal/expulsion or pregnancy, whichever comes earlier, excluding the following (unless the subject became pregnant in the cycle):

- Cycles where back-up contraception or emergency contraception use was reported by the subject;

- Cycles with no intercourse.

The cycle is defined as 28 days with the day of study device successful placement as cycle 1 day 1. The last cycle of pregnancy risk can be a partial cycle and the number of cycles can have one decimal place. The number of cycles (NC) of pregnancy risk for each subject will be calculated as:

$$NC = \frac{\min(\text{Date of removal/expulsion, Date of conception}) - \text{Date of placement}}{28}$$

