Reference: Listing xxx.

Program Location: \\xx\xxx\xxx\xxx\xxxxxx\xxxxxxxxxxxxxxxxxxxx\xxxx\xxxxx.sas

date

time

Table 14.3.5.4
Transvaginal Ultrasound (Safety Population)

	All Subjects (N=xx)
Device in Place	
n	n (%)
Yes	n (%)
No	n (%)

Reference: Listing xxx.

Program Location: \\xx\xxx\xxx\xxx\xxxxxx\xxxxxxxxxxxxxxxx\xxxx\xxxxx.sas date time

CONFIDENTIAL

Sebela Pharmaceuticals Development LLC
CMDOC-0022

Page x of y

Table 14.3.6.1.1
Bleeding and Spotting by Cycle (Safety Population)

Number of Days With	Cycle Statistic	All Subjects (N=xx)
Bleeding or Spotting	Cycle 1	
	n	xx
	Mean	xx.x
	SD	xx.xx
	Median	xx.x
	Min	xx
	Max	xx
	xxxxx	
	n	xx
	Mean	xx.x
	SD	xx.xx
	Median	xx.x
	Min	xx
	Max	xx
None		
Spotting		
Light Bleeding		
Medium Bleeding		
Heavy Bleeding		
Bleeding		
Heavier Flow than when not Using Hormones		
Heavier Flow than when not Using Hormones when Bleeding occurred		

CONFIDENTIAL

Note: Bleeding include Light Bleeding, Medium Bleeding and Heavy Bleeding.

Note: Menses question has the following choices: None, Spotting (minimal bleeding, no sanitary products required), Light Bleeding (pad, liner, or tampon used), Medium Bleeding (pad, liner, or tampon used), Heavy Bleeding (pad, liner, or tampon used).

Note: The heavy flow question is only asked when the subject responds with Spotting, Light Bleeding, Medium Bleeding, or Heavy Bleeding to the menses question.

Reference: Listing xxx.

Program Location: \\xx\xxx\xxx\xxx\xxxxxx\xxxxxxxxxxxxxxxxxxxx\xxxx\xxxxx.sas

date

time

Programmer note:

1. Table will continue with all cycles and remaining symptom.

2. Follow a similar format as Table 16.3.6.1.1 for:

Table 16.3.6.1.2 Bleeding and Spotting by Cycle (ECYC Population)

CONFIDENTIAL

Sebela Pharmaceuticals Development LLC
CMDOC-0022

Page x of y

Table 14.3.6.2.1
Occurrence and Severity of Dyspareunia in Number of Days by Cycle (Safety Population)

Cycle Statistic	All Subjects (N=xx)					
	No Pain	Some Pain	Painful	Moderately Painful	Very Painful	Not Applicable
Cycle 1						
n	xx	xx	xx	xx	xx	xx
Mean	xx.x	xx.x	xx.x	xx.x	xx.x	xx.x
SD	xx.xx	xx.xx	xx.xx	xx.xx	xx.xx	xx.xx
Median	xx.x	xx.x	xx.x	xx.x	xx.x	xx.x
Min	xx	xx	xx	xx	xx	xx
Max	xx	xx	xx	xx	xx	xx
xxxxx						
n	xx	xx	xx	xx	xx	xx
Mean	xx.x	xx.x	xx.x	xx.x	xx.x	xx.x
SD	xx.xx	xx.xx	xx.xx	xx.xx	xx.xx	xx.xx
Median	xx.x	xx.x	xx.x	xx.x	xx.x	xx.x
Min	xx	xx	xx	xx	xx	xx
Max	xx	xx	xx	xx	xx	xx

Reference: Listing xxx.

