16.2.7.2 Adverse Events Related to Study Device (All Enrolled Subjects)

16.2.7.3 Adverse Events Related to Study Device Placement/Removal Procedure (All Enrolled Subjects)

16.2.7.4 Adverse Events Leading to Study Device Removal (All Enrolled Subjects)

16.2.7.5 Adverse Events Leading to Death (All Enrolled Subjects)

Listing 16.2.8.1
Subject Diary (All Enrolled Subjects)
Part 1 of 2

CONFIDENTIAL

Question ID	Question Description	Responses Description
QS1	Did you have a period (Menses) or other vaginal bleeding today?	None - None(No bleeding or spotting); Spotting - Spotting(minimal bleeding, no sanitary products required); Light Bleeding - Light Bleeding(pad, liner, or tampon used); Medium Bleeding - Medium Bleeding(pad, liner, or tampon used); Heavy Bleeding - Heavy Bleeding(pad, liner, or tampon used).
QS2	If vaginal bleeding occurred, was the flow today heavier than when you are not using hormones?	Yes; No.
QS3	Do you have vaginal intercourse today?	Yes; No.
QS4	If you have vaginal intercourse, did you experience pain during intercourse?	No Pain; Some Pain; Painful; Moderately Painful; Very Painful; Not Applicable.
QS5	If you had pain with intercourse, was the pain worse than before IUD insertion?	Yes; No.
QS6	If you have vaginal intercourse, did you use any additional birth control methods?	Yes; No.
QS7	If additional birth control methods were used, please mark all that apply:	Hormonal contraception (e.g., pill, patches, ring); Emergency contraception (e.g., Plan B, Ella); Female barrier (e.g., condom, Spermicide, cap); Male condom Alone; Male condom with Spermicide; Withdrawal; Other(specify).
QS8	Have you experienced any menstrual pain or cramping?	None; Mild; Moderate; Severe.
QS9	If pain or cramping occurred, was the cramping worse than when you are not using hormones?	Yes; No.
QS10	Did the LevoCept device expel?	Yes; No; Suspected.

CONFIDENTIAL

Sebela Pharmaceuticals Development LLC
CMDOC-0022

Page x of y

Listing 16.2.8.1
Subject Diary (All Enrolled Subjects)
Part 2 of 2

Subject ID	Date	Sequence #	Cycle #	Day #	QS1	QS2	QS3	QS4	QS5	QS6	QS7	QS8	QS9	QS10
xxx-xxx	YYYY-MM-DD	xx	xx	xx	None		Yes	No Pain	Yes	Yes	Hormonal contraception	None	Yes	Yes
	YYYY-MM-DD	xx	xx	xx	Spotting		Yes	Some Pain	Yes	Yes	Emergency contraception	Mild	Yes	Yes
	YYYY-MM-DD	xx	xx	xx	Light Bleeding	Yes	Yes	Painful	Yes	Yes	Female barrier	Moderate	Yes	Yes
	YYYY-MM-DD	xx	xx	xx	Medium Bleeding	No	No	Not Applicable	Yes	Yes	Male condom Alone	Severe	Yes	Yes

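### Dyspareunia days are counted per 28-day cycle although pain can be observed only on intercourse days, and no per-woman proportion of intercourse days with pain is planned

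*SAP*

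**What the plan says.** SAP 6.2.9.5 sets the main dyspareunia summary: "The summary will present the number of days in each cycle with dyspareunia". The cycle is calendar time (SAP 4.1): "The cycle is defined as 28 days with the day of study device successful placement as cycle 1 day 1".

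The diary items are in SAP Listing 16.2.8.1. QS3 asks "Do you have vaginal intercourse today". QS4 is conditional on it: "If you have vaginal intercourse, did you experience pain during intercourse". The permitted answers to QS4 are "No Pain; Some Pain; Painful; Moderately Painful; Very Painful; Not Applicable". The sample rows of that listing pair intercourse = No with Not Applicable.

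Tables 14.3.6.2.1 (safety population) and 14.3.6.2.2 (ECYC population) give n, mean, SD, median, minimum and maximum of the number of days per cycle, with one column for each of these six answers. SAP 6.2.9.5 adds a second type of summary: "The worst pain grade and the highest frequency occurrence pain grade in each cycle will be summarized using shift tables to assess changes from baseline". Footnotes to the shift tables restrict the percentages to women with a baseline grade and a non-missing grade in the cycle.

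Missing days follow the rule of SAP 6.2.9.4. If a cycle has at least 14 but fewer than 28 days of data, the day count is scaled up to 28 days and rounded. Pain and intercourse on missed diary days can also be recovered through the monthly contact form.

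**The concern.** Pain can be reported only on a day with intercourse, so the number of painful days is the product of two things: how often a woman has intercourse, and how often it hurts when she does. The planned count does not separate them. If intercourse becomes less frequent over successive cycles for any reason, the painful-day columns drift down and can be read as improving tolerability. If pain itself were a reason for less intercourse, the bias would run in the flattering direction.

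Intercourse frequency may vary widely between women, since eligibility asks only that a woman expect "to have coitus at least once monthly during the study period" (Protocol 8.1). The SAP handles similar situations elsewhere. For the conditional diary question on heavier flow, Table 14.3.6.1.1 has a separate row restricted to occasions when bleeding occurred. The Pearl Index leaves out cycles without intercourse (SAP 4.1). Dyspareunia gets no comparable treatment.

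**Working it through.** **Inputs.** From the documents: a 28-day cycle (SAP 4.1), pain asked only if intercourse occurred (QS4), and the imputation rule (SAP 6.2.9.4). Assumed, because the documents give no values: k = intercourse days per cycle and p = probability of pain on an intercourse day.

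**1. The SAP's own figure.** The only worked number tied to this summary is the imputation example, with 20 diary days of which 3 have the symptom: 3 + (3/20) × (28 − 20) = 4.2, which rounds to 4. It reproduces.

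**2. Share of the cycle in which pain is observable.** This is k/28. For k = 4 it is 14%; for k = 12 it is 43%.

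**3. Expected painful days = k × p.**

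| p | k = 12 | k = 8 | k = 4 | k = 2 |
|---|---|---|---|---|
| 0.10 | 1.2 | 0.8 | 0.4 | 0.2 |
| 0.25 | 3.0 | 2.0 | 1.0 | 0.5 |
| 0.50 | 6.0 | 4.0 | 2.0 | 1.0 |

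Along each row pain per intercourse day is constant, yet the count falls in proportion to k. From k = 8 to k = 6 the fall is (8p − 6p)/8p = 25%, whatever p is.

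**4. Falling frequency with rising pain.** If p doubles, the count still falls when k₁ × 2p < k₀ × p, that is, when k₁/k₀ < 0.5. For one woman: 3 painful of 12 intercourse days, then 2 painful of 4. The count goes from 3 to 2 while the proportion goes from 25% to 50%.

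**5. Worst-grade shift table.** If days are independent, the chance of at least one painful day is 1 − (1 − p)^k. At p = 0.25 it is 97% for k = 12, 68% for k = 4 and 44% for k = 2. This summary also depends on frequency. The most frequent grade does not fall mechanically with k.

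**6. Imputation.** Suppose the scaling rule is applied to each column separately. Take a cycle with 20 days of data: 14 Not Applicable, 3 No Pain, and 1 day in each of three pain grades. Multiplying by 28/20 = 1.4 gives 19.6, 4.2, 1.4, 1.4 and 1.4, which round to 20, 4, 1, 1 and 1. The total is 27 days, not 28. The painful share of intercourse days moves from 3/6 = 50% to 3/7 = 43%. The rule scales to 28 diary days, not to intercourse days, so the imputed columns are not a clean source for a proportion.

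**The case against.** The strongest reply is that the cited tables already show exposure. A day without intercourse falls under Not Applicable and a pain-free day with intercourse under No Pain. A reader might infer that a woman with no intercourse looks the same as one with frequent pain-free intercourse. Across the whole table row she does not; only the pain-grade columns agree.

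Nor is an offsetting change invisible. Let frequency fall from 9 to 6 days while the painful share rises from 20% to 30%:

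| | No Pain | Painful, all grades | Not Applicable |
|---|---|---|---|
| k = 9, p = 0.20 | 7.2 | 1.8 | 19 |
| k = 6, p = 0.30 | 4.2 | 1.8 | 22 |

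The painful days stay at 1.8, but the other two columns move, and a reader can form 1.8/9 = 20% against 1.8/6 = 30%, provided n is the same across columns. This objection stands at group level. It does not yield a per-woman proportion, its median or its spread.

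Second, the shift tables compare each woman with her own baseline, and the most-frequent-grade version is much less sensitive to frequency. That also stands, with two limits: it can miss a minority of painful days, and on a plain reading of the footnote a woman with no graded day in a cycle drops out, which leaves some selection. QS5 asks whether pain is worse than before insertion, but no table in the SAP index is assigned to it.

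Third, the stakes are low. Dyspareunia is not among the outcome measures in Protocol 5.2, SAP 6.2.9 plans no inferential safety analysis, and dyspareunia is also on the list of adverse events given special attention in Protocol 20.7. Days of pain per cycle is also a legitimate measure of burden.

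**Conclusion.** The point holds in a limited form. The painful-day columns confound intercourse frequency with pain per intercourse day, the worst-grade shift table shares part of that dependence, and no planned output gives a per-woman proportion. The SAP also leaves open how a cycle without intercourse enters the day count.

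The direction follows from the definitions. The size does not: every k and p used here is an assumption, and the effect in this trial cannot be estimated from the documents.

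Three stronger readings are not supported:

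- **No-intercourse cycles count as zero painful days.** The SAP does not say so. The 9.2% in the Protocol's sample-size assumptions pools cycles without intercourse and cycles with back-up contraception, so the share without intercourse could be anywhere from 0 to 9.2%.
- **Women avoid intercourse because of pain.** This is a possible mechanism, not something the documents record.
- **The plan cannot tell whether intercourse becomes painful.** The shift tables and the No Pain and Not Applicable columns give a partial answer.

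This is a cheap improvement to a descriptive tolerability summary. No primary result, error rate or sample size depends on it.

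**What to change.** Keep the day counts. In SAP 6.2.9.5 and Tables 14.3.6.2.1 and 14.3.6.2.2:

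- Add, for each woman-cycle with at least one intercourse day, the percentage of observed intercourse days with any pain and with each grade. The denominator is days with QS3 = Yes, including missed diary days recovered on the CRF.
- Calculate this percentage without imputation.
- Show the number of intercourse days per cycle beside it.
- State that cycles with no intercourse are not evaluable for this percentage, and state how they enter the existing day count.

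QS3, QS4 and the missed-diary form already supply the data. The cost is a few more table rows and slightly fewer evaluable woman-cycles for the new percentage.

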3. First week of e-diary training, prior to LevoCept placement, to be used as training with the subject. This e-diary data is not a part of data collection or analysis. It is intended to ensure the subject understands how to complete the e-diary during the follow up period.
4. Urine pregnancy test will be done 17 days after removal/study exit by the subject at home, with a follow up call by the study coordinator or PI required to document the results.  
**Note:** If LevoCept is removed before 52 $\pm$ 2 weeks, Visit 6 activities should be completed for Exit Visit.
5. Screening for cervical infections is required unless negative results have been obtained within three months of the screening visit.
6. Current with ASCCP cervical cancer screening guidelines. for subjects who will be 21 or older at time of informed consent
7. Insertion can occur without receipt of test results if there is no clinical evidence of infection.
8. If a subject believes the study device may have been expelled or is no longer in place, the subject should call for an urgent study visit and refrain from having sex or use appropriate non-hormonal contraception until further evaluation is completed.
9. For subjects exiting the study due to IUD expulsion: A urine pregnancy test will be done approximately 6-8 weeks after the exit visit by the subject at home, with a follow up call by the study coordinator or PI required to document results

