3.2 Study Sample Size

No formal sample size calculations were performed for the study. It is estimated that with 225 subjects enrolled with ages 18-35, a 12-month (13 cycles) Pearl Index of 0.6 (1 observed pregnancy), and 2,015 evaluable cycles, we will observe a 95% confidence interval (CI) for the 12-month Pearl Index of (0.1, 3.3).

4 Primary Efficacy and Safety Variables

For all change from baseline variables, baseline is defined as the last non-missing value on or before the day of study device successful placement. Change from baseline to post-baseline will be calculated as the post-baseline value minus the baseline value. If either the baseline or post-baseline value is missing for a particular variable, change from baseline will be missing.

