4.2 Safety and other Variables

Safety and other measures are study device placement, safety, and tolerability.

1. Placement success

Device successfully deployed at first try rate is defined as the percentage of the number of subjects with successful deployment at first attempt among the total number of subjects with first attempt.

Device successfully deployed at second try rate is defined as the percentage of the number of subjects with successful deployment at second attempt among the total number of subjects with second attempt.

Device successfully deployed rate is defined as the percentage of the number of subjects with successful deployment in either first or second attempt among the total number of subjects enrolled.

2. Ease of placement

Five categories of how easy the device placement have been collected: Very easy, Easy, Neither Easy nor Hard, Hard and Very Hard.

Five categories of device placement pain as rated by the subject: No Pain, Some Pain, Painful, Moderately Painful and Very Painful.

Question of insertions requiring mechanical cervical dilatation has been collected.

3. Adverse events

All Adverse Events (AEs) will be coded from verbatim text to PTs and grouped by system organ class (SOC) using the Medical Dictionary for Regulatory Activities (MedDRA) (version 17.0). AEs will be collected from the beginning of the study device placement procedure through to study exit. Pre-existing conditions that worsen during a study are to be reported as AEs.

Throughout the study, all AEs will be evaluated by the investigator and noted in the AE section of the CRF.

AEs will be classified as not related, unlikely related, probably related, or related events when considering their relationship to study device, study device placement/removal procedure. Also, AEs will be classified as mild, moderate, severe when considering their severity. If the severity or relationship of an AE is missing, the severity/relationship will be coded as severe, related, respectively, i.e. worst case scenario.

Treatment-emergent AEs (TEAEs): AEs that develop or that worsen in intensity during or after the exposure to the study device.

See Appendix 1 for handling of partial dates for AEs. If it cannot be determined whether the AE is treatment emergent due to a partial onset date then it will be counted as such.

Other AE variables include study device related AEs, AEs leading to study withdrawal, AEs leading to deaths, life threatening AEs, and serious AEs (SAEs).

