CONFIDENTIAL

Sebela Pharmaceuticals Development LLC
CMDOC-0022

Page x of y

Table 14.1.6
Demographics and Baseline Characteristics (All Enrolled Subjects)

Programmers note: Continued table

Characteristic	All Subjects (N=xx)
Marital Status	
Married	n (%)
Divorced	n (%)
Separated	n (%)
Single	n (%)
Widowed	n (%)
Parity	
Parous	n (%)
Nulliparous	n (%)
Weight (kg)	
...	
Height (cm)	
...	
BMI (kg/m2)	
...	
BMI Category	
Underweight (<18.5)	n (%)
Normal (18.5-24.9)	n (%)
Overweight (25.0-29.9)	n (%)
Obese (>=30)	n (%)

Note: Percentages are based on the number of subjects specified in the column header, i.e. N, unless otherwise specified.

Note: For subjects [REDACTED] without study device successfully placed, baseline weight, height and BMI are defined as last non-missing value on or before the day of later study device placement attempt.

[1] Age (years) = (Date of informed consent - Date of birth) / 365.25, rounded down to the nearest year.

[2] Subjects could mark more than one race.

BMI = Body Mass Index; Max = Maximum; Min = Minimum; SD = Standard Deviation.

Reference: Listing xxx.

Program Location: \\xx\xxx\xxx\xxx\xxxxxx\xxxxxxxxxxxxxxxx\xxxx\xxxxx.sas date time

Programmers note: Table will continue summary statistics for Weight, height, and BMI, as shown for Age.

CONFIDENTIAL

Sebela Pharmaceuticals Development LLC
CMDOC-0022

Page x of y

Table 14.1.7
Medical History (All Enrolled Subjects)

Body System	All Subjects (N=xx) n (%)
Allergies (including intolerance to nickel and copper)	n (%)
Cardiovascular	n (%)
Gastrointestinal	n (%)
Thyroid	n (%)
HEENT	n (%)
Hematological	n (%)
Hepatobiliary	n (%)
Immunological	n (%)
Integumentary	n (%)
Lymphatic	n (%)
Musculoskeletal	n (%)
Neurological	n (%)
Reproductive/Gynecologic	n (%)
Respiratory	n (%)
Urinary	n (%)
Endocrine	n (%)
Other	n (%)

Note: Subject reporting the same body system multiple times will be counted only once for that body system.

Reference: Listing xxx.

Program Location: \\xx\xxx\xxx\xxx\xxxxxx\xxxxxxxxxxxxxxxx\xxxx\xxxxx.sas

date

time

CONFIDENTIAL

Sebela Pharmaceuticals Development LLC
CMDOC-0022

Page x of y

Table 14.1.8
Gynecological History (All Enrolled Subjects)

Description	All Subjects (N=xx) n (%)
Pain During Intercourse	
No Pain	n (%)
Some Pain	n (%)
Painful	n (%)
Moderately Painful	n (%)
Very Painful	n (%)
Missing	n (%)
Prior Contraception[1]	
Oral Contraception	n (%)
Double Barrier Method	n (%)
Injectable	n (%)
Implantable	n (%)
Condom	n (%)
IUD	n (%)
None	n (%)

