Program Location: \\xx\xxx\xxx\xxx\xxxxxx\xxxxxxxxxxxxxxxx\xxxx\xxxxx.sas date time

Programmer note:
1. Table will continue with all cycles.
2. Follow a similar format as Table 16.3.6.2.1 for:
Table 16.3.6.2.2 Occurrence and Severity of Dyspareunia in Number of Days by Cycle (ECYC Population)

CONFIDENTIAL

Sebelo Pharmaceuticals Development LLC
CMD0C-0022

Page x of y

Table 14.3.6.2.3
Occurrence and Severity of Dyspareunia – Worst Pain Grade Shift from Baseline by Cycle (Safety Population)

Cycle Worst Post-Baseline Pain Grade	Baseline				
	No Pain	Some Pain	Painful	Moderately Painful	Very Painful
Cycle 1 (n=xx)					
No Pain	n (%)	n (%)	n (%)	n (%)	n (%)
Some Pain	n (%)	n (%)	n (%)	n (%)	n (%)
Painful	n (%)	n (%)	n (%)	n (%)	n (%)
Moderately Painful	n (%)	n (%)	n (%)	n (%)	n (%)
Very Painful	n (%)	n (%)	n (%)	n (%)	n (%)
Cycle 2 (n=xx)					
No Pain	n (%)	n (%)	n (%)	n (%)	n (%)
Some Pain	n (%)	n (%)	n (%)	n (%)	n (%)
Painful	n (%)	n (%)	n (%)	n (%)	n (%)
Moderately Painful	n (%)	n (%)	n (%)	n (%)	n (%)
Very Painful	n (%)	n (%)	n (%)	n (%)	n (%)

Note: At each cycle, subjects reporting more than one pain grade are counted only once using the worst severity.

Note: The denominator of the percentages is the number of subjects who have baseline and non-missing post-baseline at the corresponding cycle.

Reference: Listing xxx.

Program Location: \\xx\xxx\xxx\xxx\xxxxxx\xxxxxxxxxxxxxxxx\xxxx\xxxxx.sas

date

time

Programmer note:

1. Table will continue with all cycles.

2. Follow a similar format as Table 16.3.6.2.3 for:

Table 16.3.6.2.4 Occurrence and Severity of Dyspareunia – Worst Pain Grade Shift from Baseline by Cycle (ECYC Population)

CONFIDENTIAL

Sebelo Pharmaceuticals Development LLC
CMDOC-0022

Page x of y

Table 14.3.6.2.5
Occurrence and Severity of Dyspareunia – Highest Frequency of Occurrence Pain Grade Shift from Baseline by Cycle (Safety Population)

Cycle Highest Frequency of Occurrence Post- Baseline Pain Grade	Baseline				
	No Pain	Some Pain	Painful	Moderately Painful	Very Painful
Cycle 1 (n=xx)					
No Pain	n (%)	n (%)	n (%)	n (%)	n (%)
Some Pain	n (%)	n (%)	n (%)	n (%)	n (%)
Painful	n (%)	n (%)	n (%)	n (%)	n (%)
Moderately Painful	n (%)	n (%)	n (%)	n (%)	n (%)
Very Painful	n (%)	n (%)	n (%)	n (%)	n (%)
Cycle 2 (n=xx)					
No Pain	n (%)	n (%)	n (%)	n (%)	n (%)
Some Pain	n (%)	n (%)	n (%)	n (%)	n (%)
Painful	n (%)	n (%)	n (%)	n (%)	n (%)
Moderately Painful	n (%)	n (%)	n (%)	n (%)	n (%)
Very Painful	n (%)	n (%)	n (%)	n (%)	n (%)

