Note: At each cycle, subjects reporting more than one pain grade are counted only once using the highest frequency of severity and worst severity, in case of ties.
Note: The denominator of the percentages is the number of subjects who have baseline and non-missing post-baseline at the corresponding cycle.

Reference: Listing xxx.

Program Location: \\xx\xxx\xxx\xxx\xxxxxx\xxxxxxxxxxxxxxxxxxxx\xxxx\xxxxx.sas date time

Programmer note:

1. Table will continue with all cycles.

2. Follow a similar format as Table 16.3.6.2.5 for:

Table 16.3.6.2.6 Occurrence and Severity of Dyspareunia – Highest Frequency of Occurrence Pain Grade Shift from Baseline by Cycle (ECYC Population)

CONFIDENTIAL

Sebela Pharmaceuticals Development LLC
CMDOC-0022

Page x of y

Table 14.3.6.3.1
Occurrence and Severity of Menstrual Pain or Cramping in Number of Days by Cycle (Safety Population)

Cycle Statistic	All Subjects (N=xx)			
	None	Mild	Moderate	Severe
Cycle 1				
n	xx	xx	xx	xx
Mean	xx.x	xx.x	xx.x	xx.x
SD	xx.xx	xx.xx	xx.xx	xx.xx
Median	xx.x	xx.x	xx.x	xx.x
Min	xx	xx	xx	xx
Max	xx	xx	xx	xx
xxxxx				
n	xx	xx	xx	xx
Mean	xx.x	xx.x	xx.x	xx.x
SD	xx.xx	xx.xx	xx.xx	xx.xx
Median	xx.x	xx.x	xx.x	xx.x
Min	xx	xx	xx	xx
Max	xx	xx	xx	xx

Reference: Listing xxx.

Program Location: \\xx\xxx\xxx\xxx\xxxxxx\xxxxxxxxxxxxxxxx\xxxx\xxxxx.sas

date

time

Programmer note:

1. Table will continue with all cycles.

2. Follow a similar format as Table 16.3.6.3.1 for:

Table 16.3.6.3.2 Occurrence and Severity of Menstrual Pain or Cramping in Number of Days by Cycle (ECYC Population)

CONFIDENTIAL

Sebela Pharmaceuticals Development LLC
CMDOC-0022

Page x of y

Table 14.3.6.3.3
Occurrence and Severity of Menstrual Pain or Cramping by Cycle (Safety Population)

Cycle	All Subjects (N=xx)							
	Worst Pain Grade[1]				Highest Frequency of Occurrence Pain Grade[2]			
	None	Mild	Moderate	Severe	None	Mild	Moderate	Severe
Cycle 1	n (%)	n (%)	n (%)	n (%)	n (%)	n (%)	n (%)	n (%)
Cycle 2	n (%)	n (%)	n (%)	n (%)	n (%)	n (%)	n (%)	n (%)

[1]: At each cycle, subjects reporting more than one pain grade are counted only once using the worst severity.

[2]: At each cycle, subjects reporting more than one pain grade are counted only once using the highest frequency of severity and worst severity, in case of ties.

Reference: Listing xxx.

Program Location: \\xx\xxx\xxx\xxx\xxxxxx\xxxxxxxxxxxxxxxx\xxxx\xxxxx.sas

date

time

Programmer note:

1. Table will continue with all cycles.

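### The worst-grade dyspareunia shift tables set one baseline rating, of unnamed source, against a per-cycle maximum, so they tend to show net worsening when nothing has changed

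*SAP*

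**What the plan says.** SAP 6.2.9.5 plans three kinds of dyspareunia summary by cycle: number of days at each grade (Tables 14.3.6.2.1/.2, no baseline), and two shift summaries: "The worst pain grade and the highest frequency occurrence pain grade in each cycle will be summarized using shift tables to assess changes from baseline".

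- **Worst-grade shift (14.3.6.2.3/.4).** The table note says that "subjects reporting more than one pain grade are counted only once using the worst severity".
- **Most-frequent-grade shift (14.3.6.2.5/.6).** Here women are "counted only once using the highest frequency of severity and worst severity, in case of ties".
- **Baseline.** SAP 4 gives a general rule: "baseline is defined as the last non-missing value on or before the day of study device successful placement". No text names the item that supplies the dyspareunia baseline.
- **Pre-placement diary.** Protocol Table 1, footnote 3, treats it as training: "This e-diary data is not a part of data collection or analysis". The only other pre-placement item on the same five grades is the gynecological-history entry "Pain During Intercourse" (SAP Table 14.1.8). Its wording and recall period are not given.
- **Direct change item.** Diary question QS5 (Listing 16.2.8.1) asks: "If you had pain with intercourse, was the pain worse than before IUD insertion". The missed-diary form repeats it (Listing 16.2.8.2). Neither appears in any table. The parallel bleeding item, QS2, is summarized by cycle (SAP 6.2.9.6, Table 14.3.6.1.1).

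**The concern.** The two sides of the worst-grade shift are different statistics. Before placement there is one answer; after it, the highest of as many answers as there were intercourse days in the cycle. A maximum of several ratings lies at or above any one of them. Mass therefore moves toward worse grades even if a woman's pain is drawn from the same distribution before and after. The study has a single arm, so no control group would show the same drift and expose it. At stake is how a reader interprets the pain-with-intercourse display: part or all of an apparent shift could come from the measurement and not from the device.

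**Working it through.** The documents state no figure for this analysis, so there is nothing to reproduce. The check asks what each shift table would show if pain did not change at all.

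**Inputs.** From the documents: daily ratings on five grades, one baseline value, and the maximum or the most frequent grade per cycle. Not in the documents, so assumed: the number of intercourse days per cycle, k (eligibility expects only at least one per month), the share of pain-free days, and the correlation of ratings within a woman.

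**Step 1, closed form (pain or no pain, independent days).** Let p be the chance of pain on an intercourse day, before and after.

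- P(looks worse) = (1−p)·(1−(1−p)^k)
- P(looks better) = p·(1−p)^k

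With p = 0.10:

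| k | Worse | Better |
|---|---|---|
| 1 | 0.9 × 0.1000 = 9.0% | 0.1 × 0.9000 = 9.0% |
| 2 | 0.9 × 0.1900 = 17.1% | 0.1 × 0.8100 = 8.1% |
| 4 | 0.9 × 0.3439 = 31.0% | 0.1 × 0.6561 = 6.6% |
| 8 | 0.9 × 0.5695 = 51.3% | 0.1 × 0.4305 = 4.3% |

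The table is balanced at k = 1 and tilts toward worse from k = 2.

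**Step 2, five grades with correlated days.** Independence exaggerates the effect if pain clusters within women. This step simulates 200,000 women per scenario with a latent normal model, the same distribution before and after, 90% pain-free days and a within-woman latent correlation of 0.5. The split of the painful 10% over the four painful grades moves the results by less than one percentage point.

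| k | Worst grade vs one rating: worse / better | Most frequent grade vs one rating: worse / better |
|---|---|---|
| 2 | 13.7% / 6.4% | 13.7% / 6.4% |
| 4 | 22.2% / 4.9% | 4.4% / 8.3% |
| 8 | 32.9% / 3.1% | 2.0% / 8.7% |
| 12 | 39.7% / 2.4% | 1.3% / 9.1% |

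At k = 2 the columns agree because two different grades tie and the tie goes to the worse one, so the most frequent grade equals the maximum.

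**Step 3, range.** Taking 80%, 90% or 95% pain-free days, correlation 0, 0.5 or 0.8, and k from 4 to 12, the worst-grade table shows 8.5% to 84% worse against 0.8% to 11.2% better.

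**Step 4, dependence on the baseline question** (90% pain-free, correlation 0.5).

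- If the baseline were itself the worst of k days, the worst-grade table is symmetric: 15.6% vs 15.3% at k = 4, and 19.0% vs 19.0% at k = 8.
- If it were a usual-pain rating, the worst-grade artefact is slightly larger: 36.4% vs 0.0% at k = 8. The most-frequent-grade table then shows only a small net worsening: 5.6% vs 0.7% at k = 4, and 2.7% vs 0.8% at k = 8.

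**The case against.** Much can be said for leaving this alone.

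- **Only half the shift tables are affected.** A reader might infer that all four are biased. They are not. The most-frequent-grade pair largely escapes, and the days-by-grade tables give further context. What remains is the tie rule at low counts.
- **The baseline is not shown to be a recalled usual rating.** The SAP gives an item label and nothing on wording or recall. If the question asked for worst pain over a comparable period, the artefact disappears; it also disappears at one intercourse day per cycle. This stands as a limit on the claim, but it also shows that the SAP must name the source.
- **A Day 1 diary entry as baseline is uncertain.** A reader might infer from the SAP 4 rule that an entry made on insertion day would be used. SAP 4.1 does start diary collection on that day. However, Protocol 12.1 treats diary data from screening to the day of placement as training, and Study Day 1 belongs to Cycle 1. The texts leave it ambiguous.
- **QS5 is not an unbiased replacement.** It is asked only when pain occurred, so it cannot show improvement. It also relies on the woman's own comparison in an open-label study, and counting women with any positive answer is again a maximum over days. It belongs beside the other displays, not in place of them all.
- **The grade order is consistent.** *Painful* precedes *Moderately Painful* in the shift shells, the history item and the diary. SAP 4.2 lists placement pain in the same order: "No Pain, Some Pain, Painful, Moderately Painful and Very Painful". The shells therefore imply a ranking. The wording makes the two middle grades unclear, which calls for a stated order, not for pooling them.

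**Conclusion.** The point holds for Tables 14.3.6.2.3/.4. They are offered as an assessment of change, yet they compare a single rating with a per-cycle maximum. With two or more intercourse days per cycle they tend to show net worsening under no change, unless the baseline item asked for worst pain. The central illustration is about 22% worse against 5% better at 4 intercourse days and 33% against 3% at 8. It rests on assumed pain frequency, correlation and intercourse frequency, so it shows direction and plausible range and is not a forecast.

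A reader might go further and infer that the trial's tolerability conclusion is biased against the device. The documents do not support that. Protocol 5.2 lists bleeding and spotting patterns and discontinuation under tolerability; dyspareunia is not there. SAP 6.2.9 plans no inference on safety data, and adverse-event reporting covers dyspareunia separately. The distortion runs toward showing more pain, and the Pearl Index and planned sample size are unaffected. It is a correctable fault in a secondary descriptive display.

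**What to change.** In SAP 6.2.9.5 and the matching shells:

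1. Present worst grade as a per-cycle distribution without a baseline shift, as Table 14.3.6.3.3 already does for cramping. Protocol 20.7 asks only for occurrence and severity by cycle, so no protocol content is lost. If removing planned tables is unwelcome, keep 14.3.6.2.3/.4 with a footnote that a single baseline rating is being compared with a maximum.
2. For the most-frequent-grade shift, name the gynecological-history item as baseline, with its question wording, and exclude any Day 1 diary entry.
3. Add a by-cycle table of QS5: percent of intercourse days with pain worse than before insertion, and number of women with any such day. Note that it is self-reported and cannot show improvement.
4. State the grade order used for worst grade and for ties. Do not pool the middle grades.

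Tabulating the cramping counterpart, QS9, in the same way is optional. All the data are already being collected, so the cost is SAP text, table shells and programming.
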